5.5 Early Withdrawal of Subjects

[figure not shown]
Subjects can withdraw from the study at any time for any reason if they wish to do so without any consequences or loss of benefits to which they are otherwise entitled. The investigator can decide to withdraw a subject from the study for urgent medical reasons.

Any data collected until the time of subject withdrawal may be included in the final data analysis. Information on the subject's withdrawal should be documented on the CRF and the Screening and Enrollment Log, and should include clear documentation of the reason for withdrawal. Subjects that withdraw from the study may be replaced by another volunteer.

6 STATISTICAL CONSIDERATIONS

6.1 Sample Size Calculation

The current study will be a repeated measures study with one group. The study is focused at assessing the agreement of $\text{SaO}_2/\text{SvO}_2$ readings with O3-derived rSO_2 readings during a stepped hypoxia plateau sequence protocol. A high level of correlation among repeated measures (0.9) is assumed.

The calculation(s) of the required sample size comply with formal requirements in the U.S. by the FDA, which require for NIRS validation studies the inclusion of at least 12 subjects[9].

6.2 Statistical Plan

All analyses will be performed for pooled data from all sensors, as well as broken down per individual sensor. As the aim of the study is to investigate agreement of Masimo O3 regional oximeter-derived rSO_2 readings with the invasive blood gas derived gold standard(s), conventional method comparison statistics (i.e. bias, precision and repeatability) will be performed.

Primary Study Parameter(s): The data from this study will be analyzed using a mixed effects analysis with subject as random effects terms. By adding an additional factor identifying replicate data points, the repeatability of cerebral and somatic O3 rSO_2 values ($\Delta\text{rSO}_2(\text{O3}) - \Delta\text{rSO}_2(\text{Gold Standard})$) will be estimated and used to correct Limits of Agreement for repeated measures on the same subject. Bland Altman Plots will be created showing the calculated Limits of Agreement. These will be evaluated to check whether the variance of rSO_2 from the investigated devices and the invasive gold standard, is constant over the range of hypoxia studied.

Other Study Parameter(s): To evaluate the evolution of continuous hemodynamic variables (stroke volume, arterial blood pressure) during the study protocol, the Mann-Whitney test will be used. Categorical variables (gender, skin pigmentation as assessed by the Massey scale) will be analyzed with the Fisher's Exact test.

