3 STUDY OBJECTIVES

3.1 Primary Objective

The primary objective is to validate Masimo O3 regional oximeter-derived somatic rSO₂ readings in healthy volunteers under controlled hypoxia, by comparison of these readings with SaO₂ / SvO₂ blood reference values as the gold standard.

[REDACTED]

[REDACTED]

[REDACTED]

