4.2 Study Endpoints

4.2.1 Primary Endpoint

The primary endpoint for this study is to assess regional oximeter-derived somatic rSO₂ with Masimo O3 sensors and to compare this to invasively determined somatic oxygenation values (SaO₂ / SvO₂) during normoxia and

controlled hypoxia [REDACTED]
[REDACTED]
[REDACTED]
[REDACTED]

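### Section 6.2 checks only constant variance over the hypoxia range; it should also estimate how bias changes with oxygen level, and make the pooled primary estimate somatic

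*Combined protocol and SAP*

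**What the plan says.** The primary objective (3.1) is to "validate Masimo O3 regional oximeter-derived somatic rSO₂ readings in healthy volunteers under controlled hypoxia", and the primary endpoint (4.2.1) is "to assess regional oximeter-derived somatic rSO₂ with Masimo O3 sensors" against invasive values in normoxia and in controlled hypoxia. Section 1.1 stresses that readings must be dependable across oxygenation states, above all in hypoxia.

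Section 6.2 names bias, precision and repeatability as the agreement statistics, from a mixed model with subject as a random effect. "By adding an additional factor identifying replicate data points", "the repeatability of cerebral and somatic O3 rSO_2 values" is obtained from a difference of Δ values (O3 minus gold standard). It "will be estimated and used to correct Limits of Agreement for repeated measures on the same subject". Bland-Altman plots with these limits are then used to "check whether the variance of rSO_2 from the investigated devices and the invasive gold standard, is constant over the range of hypoxia studied". The section states no fixed effect for plateau or saturation, no slope of the difference, no limits by level, and no rule for what follows if the check fails. Neither Δ nor the replicate factor is defined in the visible text.

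On pooling, 6.2 says: "All analyses will be performed for pooled data from all sensors, as well as broken down per individual sensor". Section 5.4 allows rSO₂ sensors on the forehead as an option.

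**The concern.** Constant variance and constant bias are separate conditions for one set of limits to describe a device over its whole range. Section 6.2 names only the first. If O3 minus reference moves from positive at normoxia to negative at the deepest plateau, or the reverse, the overall bias can sit near zero. At the lowest plateau the device would then misread mainly in one direction. That is the part of the range that section 1.1 singles out, and the reported result would carry no figure for it.

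The secondary question is site. The objective and endpoint are somatic, but the only pooled result is over all sensors. If forehead readings are counted there and their error differs, the pooled figure partly reflects how many forehead sensors were applied.

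**Working it through.** Section 6.2 gives no numerical result to reproduce, so the check is an illustration.

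**Inputs.** From the documents: 25 subjects (4.1, 4.5). Assumed, because the hypoxia levels are blacked out and no SD is given: five equally weighted levels, normal errors with SD 4 at every level, and bias falling linearly from +4 to −4 points (biases +4, +2, 0, −2, −4) or from +2 to −2 (+2, +1, 0, −1, −2). Between-level variation is taken to stay in the overall limits.

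**The stated check.** Variance is 16 at every level in both cases, so constancy of variance holds exactly. A formal test of variance centred within level would ignore drift by construction.

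**Overall limits.** Pooled SD = √(SD² + variance of the level biases); limits = mean bias (0) ± 1.96 × pooled SD.
- Larger drift: variance of biases = (16+4+0+4+16)/5 = 8; pooled SD = √24 = 4.899; limits ±9.60.
- Smaller drift: (4+1+0+1+4)/5 = 2; pooled SD = √18 = 4.243; limits ±8.32.

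**At the lowest level.** Its own limits are level bias ± 1.96 × 4.
- Larger drift: −4 ± 7.84 = −11.8 to +3.8. Share below the overall lower limit = Φ((−9.60+4)/4) = 8.1%; share above the upper = 0.03%; coverage 91.9%.
- Smaller drift: −2 ± 7.84 = −9.8 to +5.8. Share below = Φ((−8.32+2)/4) = 5.7%; above = 0.5%; coverage 93.8%.
- With SD from 3 to 5, the share below is 8.7% to 7.3% (larger drift) and 6.7% to 5.1% (smaller drift).

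**Over the whole range.** Mean coverage of the overall limits across the five levels:
- Larger drift: (91.9 + 97.0 + 98.4 + 97.0 + 91.9)/5 ≈ 95.2%.
- Smaller drift: (93.8 + 95.6 + 96.2 + 95.6 + 93.8)/5 = 95.0%.

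The limits widen enough to absorb the drift on average; what remains is a one-sided excess at the ends of the range.

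**What 25 subjects can estimate** (one pair per level).
- Slope SE per level step, common slope, independent errors: 4/√(25 × 10) = 0.253. The total drift spans four steps, so its 95% half-width is 1.96 × 4 × 0.253 = ±2.0 points.
- If slopes vary between subjects by an assumed SD of 1 point per level: SE = √(0.253² + 1/25) = 0.322, giving ±2.5 points.
- One limit at one plateau: SE = 4 × √(1/25 + 1.96²/48) = 1.386, giving ±2.7 points.

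**Site pooling.** The shift in pooled bias is forehead share × site difference. With an assumed one-third share and a 3-point difference, it is 1.0 point.

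**The case against.** The strongest reply is that an overall figure suits an endpoint covering normoxia and hypoxia, and that the overall limits keep their nominal coverage over that range. This stands. A reader might infer that the planned limits under-cover in general; the 95.2% and 95.0% above show that they do not. The 92% and 94% figures apply at the lowest level only.

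Second, an analyst looking at a difference plot would probably notice a sloping cloud. This also stands in part. The documents do not support saying that drift would go undetected, only that the plan names no estimate, test or consequence for it.

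Third, the Δ comparison might carry drift information. It could, if Δ is change from baseline and is reported by level. But Δ is undefined, and 6.2 uses it only for repeatability and for correcting the limits. It is likewise tempting to assume that the replicate factor strips out plateau variation and makes the limits too narrow at the extremes. The text does not say what the factor indexes, so that cannot be claimed.

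Fourth, section 6.1 says "A high level of correlation among repeated measures (0.9) is assumed", which would suggest a much tighter drift estimate. That value is not stated to apply to O3-minus-reference errors, so I do not rely on it.

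On site, a reader might infer that the primary result will be contaminated by cerebral readings. That needs forehead sensors to be used, counted among all sensors, given a reference, and to differ in error. The wording on cerebral and somatic values is compatible with separate estimates, per-sensor results are already planned, and blacked-out text may cover cerebral readings.

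**Conclusion.** The point holds as a gap in the stated analysis: in the visible text of 6.2, variance is the only property checked over the hypoxia range, and constancy of bias is not addressed. Under the assumed five levels and SD 4, a drift of +4 to −4 points puts 8.1% of errors at the lowest level below the overall lower limit, and +2 to −2 puts 5.7% there, against a nominal 2.5%. Apart from the 25 subjects, the numerical inputs are assumptions, and there is no distortion if bias is constant. The overall limits are not invalid, and nothing here shows that the device does drift.

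The pooling question is secondary and conditional. With one somatic sensor per subject, the per-sensor result already is the somatic estimate; with several, no pooled somatic estimate is defined. Rated as a cheap improvement.

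**What to change.** In section 6.2:
- Add plateau or reference saturation as a fixed effect in the mixed model for O3 minus reference, with subject-specific slopes if the data support them.
- Report the slope of bias with its confidence interval, and check it alongside variance.
- Report regression-based or per-plateau bias and limits beside the overall figure, and state that they will be relied on if bias or variance is not constant.
- Define Δ and the replicate factor.
- Secondary: state whether forehead data enter the pool. If forehead sensors are used, make the primary pooled estimate somatic sensors only and report forehead results separately. They need not be dropped if a blacked-out objective covers them.

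The cost is wording and a few more tables, with no extra subjects, samples or procedures. The downside is precision: per-plateau limits are known only to about ±2.7 points at SD 4, and total drift to about ±2.0 to ±2.5 points under the assumptions above. That is why they belong beside the overall figure.

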The Masimo O3 regional oximeter (Masimo Corp, Irvine, USA) has been developed recently. This device allows measurement of somatic tissue oxygen saturation (rSO_2) at different sites. Obviously, it is of paramount importance that NIRS readings are reliable during different states of oxygenation, especially during hypoxia. While rSO_2 trending in somatic tissues has been assessed previously[8], and the O3 device has recently received FDA clearance and CE marking for rSO_2 trending in somatic tissues, its absolute accuracy in monitoring rSO_2 in somatic tissues has not been determined yet.

To assess whether somatic rSO_2 values match with microcirculatory oxygenation of the tissue of interest, both the afferent (arterial input) and efferent (venous output) oxygenation needs to be assessed. Hence, in absence of any major circulatory pathology that would influence arterial oxygenation, this is generally derived from a radial artery catheter (SaO_2) and from a venous catheter (SvO_2) as close to the tissue of interest as possible[9].

One study in healthy volunteers examined the absolute and trend accuracy of the O3 oximeter previously. In this study cerebral rSO_2 was measured continuously on the forehead and reference blood samples were taken from the radial artery and internal jugular bulb vein, at baseline and after inducing hypoxic states. This study enrolled 27 subjects and found acceptable absolute and trend accuracy of the rSO_2 measurements when compared with the reference gold standard. [REDACTED]

A method agreement study was also done in the clinical setting, in which peripheral somatic rSO₂ readings of the O3 device were compared with those measured with another device (EQUANOXTM 7600, Nonin Medical Inc, Plymouth, USA) in cardiac surgical patients. This study suggested that both devices cannot be used interchangeably. A limitation of this study was that the O3 device was not compared to the gold standard (gradient between arterial and venous oxygen saturation).

In this study, controlled hypoxia will be induced in healthy volunteers while Masimo O3 regional oximeter-derived rSO₂ readings of somatic tissue [REDACTED] will be measured. These readings will be compared with SaO₂ and venous sheath-derived reference SvO₂ values [REDACTED]

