5.4 Study Procedures

- O3 rSO₂ sensors will be applied before each study session.
- All subjects will have their medical history done at the time of the screening period. Female subjects will have a pregnancy test prior to being admitted to the study.
- Upon passing the screening tests, each subject will read and sign an Informed Consent to Act as a Human Research Subject form prior to being enrolled in the study.

- A (20G) radial artery catheter will be inserted in the radial artery of the non-dominant hand. It will be inserted under local anesthesia (Lidocaine), only after the Allen Test is negative. The arterial catheter will be used for SaO_2 measurements and for continuous monitoring of arterial blood pressure.

- The venous sheath and radial artery will be continuously flushed with NaCl 0.9% by a pressure infusion bag (per institutional policy).

- The Masimo O3 regional oximeter rSO₂ sensor will be placed on the skin [REDACTED]
[REDACTED]
The rSO₂ sensors may be placed on the forehead as well.

The rSO₂ sensors may be placed on the forehead as well.

- The face-mask will be applied to the subject and it will be connected to the breathing circuit. Note, the subject will still breathe room air at this moment.

- Hypoxia Plateau Sequence Protocol by changing inspiratory oxygen fraction (FiO_2):

After all catheters and sensors have been placed, the following intervention(s) will be applied during the stepped hypoxia plateau sequence:

- o Baseline blood samples will be obtained

Hypoxia breathing mixtures of O₂ / N₂ in air via a tight-fitting facemask.

- After measurements have been completed, the subject will be allowed to breathe room air.
- A study event flowchart of the stepped hypoxia plateau sequence is given below (figure 1).

- Recovery Period:

- The volunteer should remain in bed for one hour, and will be monitored using the remaining basic monitoring (see above) for another hour.
- The volunteer will be allowed to go home after the medical personnel determine that it is safe to do so. The volunteer should not drive a car by themselves, until 1 day after the study procedure. The volunteer is asked to refrain from strenuous exercise the first 48 hours after the study procedure.

- All blood samples will be immediately analyzed using satellite-lab blood gas analysis.

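### Section 6.2 plans agreement for forehead (cerebral) sensors, but the readable objective, endpoint reference and venous access are somatic, so absolute forehead and pooled agreement would mix device error with a vascular-bed difference

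*Combined protocol and SAP*

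**What the plan says.** Section 3.1 sets a somatic aim: "The primary objective is to validate Masimo O3 regional oximeter-derived somatic" readings. The primary endpoint in section 4.2.1 is somatic as well; it takes O3 readings to "compare this to invasively determined somatic oxygenation values" built from arterial and venous saturation.

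Section 5.4 nevertheless allows forehead placement: "sensors may be placed on the forehead as well". Section 7 mentions a headband for securing forehead sensors, so this is a real possibility.

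Section 6.2, under the primary study parameters, brings those readings into the analysis. It says: "By adding an additional factor identifying replicate data points, the repeatability of cerebral and somatic O3 rSO_2 values" will be estimated, defined as the change in the O3 value minus the change in the gold standard, and the result used to correct the limits of agreement. The same section asks for every analysis both pooled over all sensors and separately for each sensor. It does not say which venous reference applies to a forehead sensor.

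On the choice of reference, section 1.1 says the venous catheter should be "as close to the tissue of interest as possible". It also reports that in the earlier volunteer study of cerebral O3 readings "reference blood samples were taken from the radial artery and internal jugular bulb vein".

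The venous access described for this study is singular. Section 5.4 has one sheath ("The venous sheath and radial artery will be continuously flushed"), and section 7 describes one venous catheter and one x-ray to check its position.

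**The concern.** By the protocol's own rule, a venous reference is valid for a sensor only if it drains tissue near that sensor. One catheter cannot be near both the forehead and a separate somatic site. If the readable plan is followed, a forehead sensor is compared with venous blood from another bed.

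The per-sensor output would then present forehead bias and limits as agreement with a gold standard, when part of the disagreement is physiological. This matters most for absolute accuracy, which section 1.1 names as the open question for this device in somatic tissue. The pooled analysis would carry the same mismatch wherever forehead sensors were applied. The limits reported for the somatic objective could also be affected, but only if sites are pooled or share one repeatability estimate.

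**Working it through.** The plan states no figure for this effect, so there is none to reproduce. The sample size of 25 is not at issue here.

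**Inputs**
- Venous weight w: 0.70 or 0.75, from the 30:70 and 25:75 arterial-to-venous ratios in section 1.1. These describe NIRS devices in general. The formula for this study's reference is not readable.
- D: cerebral minus somatic venous saturation, in points. The documents give no value, so 5, 10 and 15 are assumed.
- s: between-subject SD of that difference, assumed 5.
- Device SD: assumed 4, with a range of 3 to 5.

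**1. Absolute bias.** Write the reference as (1 − w) × SaO2 + w × SvO2. The arterial part is common to both sites. Replacing cerebral with somatic venous blood therefore gives:

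apparent forehead bias = device bias + w × D

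| Assumed D | w = 0.70 | w = 0.75 |
|---|---|---|
| 5 | 3.5 | 3.75 |
| 10 | 7.0 | 7.5 |
| 15 | 10.5 | 11.25 |

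**2. Limits of agreement for a forehead sensor.** Total SD = √(device SD² + (w × s)²), and the half-width is 1.96 times that. With w = 0.70 and s = 5, (w × s)² = 3.5² = 12.25.
- Device SD 4: √(16 + 12.25) = 5.32. The half-width is 10.4, against 1.96 × 4 = 7.8 without the mismatch.
- Device SD 3: √(9 + 12.25) = 4.61. The half-width is 9.0, against 5.9.
- Device SD 5: √(25 + 12.25) = 6.10. The half-width is 12.0, against 9.8.

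**3. Pooled result.** Suppose half the readings come from the forehead, with D = 5, s = 5, device SD 4, w = 0.70 and no device bias at either site.
- Pooled bias = 0.5 × 3.5 = 1.75.
- Pooled variance = 0.5 × 28.25 + 0.5 × 16 + 0.25 × 3.5² = 25.19, so the SD is 5.0.
- Without the mismatch these would be 0 and 4.0.

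**4. Change-based repeatability.** Take the change as the difference between two time points in one subject. The mismatch then contributes w × (D at the second time − D at the first). A constant D gives zero. If D moves by 2 points between baseline and hypoxia, the contribution is 1.4 to 1.5 points; if it moves by 5, it is 3.5 to 3.75 points.

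**5. Somatic per-sensor bias.** This uses only somatic readings and the somatic reference, so D does not enter.

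**The case against.** The strongest reply is that the relevant text is blacked out. Redactions follow the objective (3.1) and the endpoint (4.2.1), and they cover details of the reference (1.1), blood sampling (5.3), sensor placement (5.4) and the vein (7). Section 6.2 also allows for more than one gold standard in its wording. A reader might infer that this study has no cerebral venous reference at all, but the documents do not support that. The single sheath, catheter and x-ray make a second venous line unlikely without excluding it. This part of the reply stands, and it makes the point conditional.

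The reply is also right that the bias shifts do not carry over to repeatability. A reader might conclude that every forehead figure is uninterpretable. However, a constant bed difference cancels in change scores, and replicate variation in the O3 readings alone needs no blood reference.

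A third tempting inference is that the somatic limits are contaminated. Section 6.2 does not say whether cerebral and somatic data share one repeatability estimate; it can equally be read as one estimate per site, and it also asks for per-sensor results. Contamination follows only if sites are pooled or share that estimate.

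Finally, forehead placement is optional, and the readable text sets no forehead acceptance criterion. That limits the importance of the point. It does not remove the need for 6.2 to say which reference a forehead sensor is compared with.

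**Conclusion.** The point holds for the readable text. Section 6.2 plans absolute agreement for forehead sensors, and a pooled figure that can include them, while the objective, the endpoint reference and the described venous access are somatic. Those results would combine device error with a bed difference of 0.70 to 0.75 points per point of venous difference.

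The size in any real dataset is unknown. It rests on background weights and on assumed values of D, s and device SD, so the figures show scale and are not estimates. They apply to absolute bias, limits and pooled agreement. For change-based repeatability, only the part of the difference that changes with hypoxia or varies within a subject matters.

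The documents do not show that the primary somatic comparison is invalid. The problem is worth correcting because the plan as written would produce a forehead accuracy figure that its readable design cannot support.

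**What to change.** Amend section 6.2 in one of two ways.
- If the full protocol provides a matched cerebral venous reference, name it for the forehead sensors and keep their agreement analysis separate from the somatic one.
- If it does not, remove the cerebral term from the repeatability estimate that corrects the limits of agreement. State that forehead sensors are excluded from both pooled and per-sensor agreement with this study's arterial and venous reference. Report forehead readings descriptively, for example as O3-only replicate variation within a plateau.

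This is a wording change with no effect on procedures or sample size. Under the second option the sponsor gives up a forehead accuracy figure, which the readable design cannot support.

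### Does the Δ expression in Section 6.2 turn the primary Limits of Agreement into a measure of trend error instead of absolute accuracy?

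*Combined protocol and SAP*

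**What the plan says.** Section 1.1 separates two properties of the device in somatic tissue. Trending is settled: "the O3 device has recently received FDA clearance and CE marking for rSO_2 trending in somatic tissues". Absolute accuracy is open: "its absolute accuracy in monitoring rSO_2 in somatic tissues has not been determined yet". Section 3.1 sets the primary objective as validating the somatic readings "by comparison of these readings with SaO₂ / SvO₂ blood reference values as the gold standard".

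Section 6.2 opens with the same aim, agreement of readings with the blood-gas reference, and states that "conventional method comparison statistics (i.e. bias, precision and repeatability) will be performed". Its primary paragraph then says: "The data from this study will be analyzed using a mixed effects analysis with subject as random effects terms". The next sentence adds a further model factor that marks replicate observations. By that means, it says, "the repeatability of cerebral and somatic O3 rSO_2 values ($\Delta\text{rSO}_2(\text{O3}) - \Delta\text{rSO}_2(\text{Gold Standard})$) will be estimated and used to correct Limits of Agreement", the correction being for repeated observations within a subject. The Bland-Altman check that follows is described for rSO₂ itself, without Δ.

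The visible text does not define Δ, does not name the outcome of the mixed model, and does not write the paired difference (O3 minus reference at one blood draw) as a formula. Parts of Sections 3.1, 4.2, 5.3 and 5.4 are blacked out, including much of the plateau and sampling detail.

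**The concern.** The only O3-versus-reference formula in the primary analysis is a difference of Δs, and Δ ordinarily means a change. A reader could take the formula as the modelled variable, on the argument that a repeatability term must belong to the variable whose limits it corrects. The primary limits would then describe how well the device follows changes, the property Section 1.1 treats as already cleared.

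The stake would be real. Any constant offset, and any fixed error within a subject, cancels from a change score. A device reading several points off in everyone would show a bias near zero. Another analyst, following the prose, would report limits on readings, and both could claim to have followed Section 6.2.

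**Working it through.** No figure in the plan is in dispute, so there is none to reproduce. The check asks what each reading of Δ does to the limits.

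**Model.** Let d = O3 − reference at one blood draw, with d = b + u + w: a constant offset b, a subject effect u with variance s²ρ, and a residual w with variance s²(1−ρ).

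**Inputs.** b = 5 points and s = 4 points are assumptions. The values of ρ (0.3 to 0.9) are assumptions too. Section 6.1 says "A high level of correlation among repeated measures (0.9) is assumed" but does not say that this applies to the O3-minus-reference errors. The simulation behind the table used 25 subjects (the planned number), a baseline plus 5 plateaus, and 2 replicates; the last two are assumed.

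**Correct target.** Limits on readings are b ± 1.96·s = 5 ± 1.96 × 4 = 5 ± 7.84.

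**Reading A: Δ is a difference between replicates.**
- ΔO3 − ΔReference = (O3₂ − O3₁) − (Ref₂ − Ref₁) = d₂ − d₁.
- Its variance is 2s²(1−ρ), and half of that is the within-subject variance of d.
- At ρ = 0.9: half of 3.2 is 1.6. Adding the subject variance of 14.4 gives 16, so the half-width is 1.96 × 4 = 7.84.
- The limits for readings are right.

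**Reading B: Δ is change from baseline, used only to estimate repeatability.**
- Within a subject the baseline residual is constant, so a subject random effect absorbs it. The residual SD of the changes is s√(1−ρ).
- At ρ = 0.9: 4 × √0.1 = 1.26, the true within-subject SD of d. The simulation also returned 1.26.
- Limits on readings corrected with this value are again right.

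**Reading C: Δ is change from baseline, and the limits themselves are run on it.**
- The mean change error is 0 for any b.
- The half-width is 1.96·s·√(2(1−ρ)).

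| ρ (assumed) | √(2(1−ρ)) | Readings: bias, half-width (simulated) | Reading C: bias, half-width (formula) | Reading C: half-width (simulated) |
|---|---|---|---|---|
| 0.3 | 1.18 | 5.0, 7.83 | 0, 9.28 | 9.25 |
| 0.5 | 1.00 | 5.0, 7.80 | 0, 7.84 | 7.82 |
| 0.7 | 0.77 | 5.0, 7.76 | 0, 6.07 | 6.06 |
| 0.9 | 0.45 | 5.0, 7.77 | 0, 3.51 | 3.48 |

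A separate simulation with an assumed SD of 5 gave practically the same change-score limits at each ρ for true offsets of 0, 5 and 10 points. So under reading C the offset is always lost, while the limits may come out narrower (ρ above 0.5) or wider (ρ below 0.5).

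**Which reading does the text support?** The sentence starts from replicate observations, names its quantity repeatability, and gives it one job, to correct the limits. Visible Section 6.2 never mentions change from baseline. Reading C also needs the analyst to set aside three things: the stated aim (agreement of readings), the promised bias statistic, and the Bland-Altman check on rSO₂ itself. Readings A and B need none of this.

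**The case for a change.** The strongest case for a change is that a primary analysis should not depend on the reader's goodwill. Δ is undefined, the model outcome is unnamed, one conceivable reading cannot detect a constant bias, and defining the paired difference would need no new data. A redacted trend endpoint might explain why a Δ term exists, but not why it is the only formula in the primary paragraph.

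Part of this stands. The symbol is undefined in the visible text and the paired difference is not written out. A clarifying line would do no harm.

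The central inference does not stand. A repeatability term built from Δ need not drag the limits onto Δ: readings A and B both give the correct within-subject variance for limits on readings. Using a Δ-based term to correct limits on readings is therefore coherent, and prose and formula do not conflict.

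Nor is rewriting the formula free of risk. A natural replacement takes within-subject variance only from replicates at the same plateau and adds between-subject variance. That drops subject-by-plateau error. With assumed variances of 8 (subject), 6 (subject-by-plateau) and 2 (replicate), the correct half-width is 1.96 × √16 = 7.84, and the shortened sum gives 1.96 × √10 = 6.20. A hasty rewrite could make the limits too narrow, an error the present wording does not impose.

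**Conclusion.** The concern does not call for a change. The arithmetic behind it is sound but conditional: if the limits were run on change from baseline, the offset would be lost entirely and the width multiplied by 0.45 to 1.18 for assumed error correlations of 0.9 to 0.3. The plan does not specify that analysis, and its stated aim, its promised statistics and the replicate clause all point to limits on readings. There the error is nil whether Δ is a replicate difference or a change from baseline used only for repeatability.

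What remains is a notational gap that a competent analyst fills correctly from the same section. This rests on the visible text; a definition of Δ or of the replicates may sit in the redacted parts. The offset, SD, correlations, number of plateaus and number of replicates are illustrative assumptions. The equivalence under reading B also assumes the simple subject-plus-residual error model used above.
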